### Exclusion Criteria:

- Active suicidal ideation (Montgomery Asberg Depression Rating Scale item 10>4)
- Inability to speak English or Spanish
- Axis 1 Diagnostic and Statistical Manual of Mental Disorders, 5th Edition (DSM-5) diagnoses other than unipolar depression or generalized anxiety disorder (by Structured Clinical Interview for DSM-5)
- Severe or life-threatening medical illness

EM emergency and or referral out of EM agency (per EM staff)

## DATA AND SAFETY MONITORING PLAN

Some participants may find the questions asked as part of the research interview to be distressing or tedious. Participants are given the option to refuse to answer any question and always have the right to withdraw from the study should they find it distressing or tedious. Participants may become seriously medically ill and decide not to participate. In addition, if new psychiatric symptoms develop or change in severity, or the abuse situation escalates, we may recommend removal from the study and provide referrals for the appropriate treatment needed. All EM victims will continue to receive EM resolution services from DFTA regardless of their participation or termination of participation in the study intervention.

14. Describe the anticipated adverse events and risks of study intervention(s), agent(s) and/or device(s) in detail (e.g., potential risk of the study drug, including potential drug interactions, psychological risks; physical risks). Assess their seriousness and incidence of complications or adverse events when known. Include animal data if trials in humans have not been performed.

Cornell research staff will assess changes in depressive symptoms at regular intervals. Patient's health and clinical care will always take priority over study participation. Participants may not want to continue completing research assessments or activities and will be free to discontinue participation at any time.

15. Given the risks identified, describe what monitoring is needed to immediately recognize the adverse events that do occur.

Study interviewers will be Weill Cornell research staff who are trained in assessments with older adults. They will specifically inquire about depressive symptoms, falls, and hospitalizations. Referring elder abuse staff are also trained to monitor the participant's mental state (in addition to abusive incidents) and will report any notice of falls, hospitalizations, and increasing symptom severity to Weill Cornell staff and the principal investigator. If any moderate to severe symptom changes (or new symptoms) are noted, we will consider alternative options to maximize the participant's well-being.

16. Describe what measures will be taken to minimize any negative impact on subjects resulting from study closure or a subject being terminated from the study.

All participants will continue to receive elder mistreatment resolution services from their referring agency if they choose to withdraw from the study. Referrals to external mental health agencies will be offered to participants who drop out of the study in order to address any ongoing depressive symptoms.

17. Describe the adverse event grading based on severity, attribution, and expectedness (including frequency) that will be used, to whom they will be reported and how often.

The study will adhere to the adverse event grading guidelines provided by Weill Cornell's Office of Research Integrity and Assurance. All adverse events will be reported to the Weill Cornell IRB in the timeline indicated by the Weill Cornell Human Research Protection Program Immediate Reporting Policy.

18. In addition to the IRB, specify to whom you will be reporting unexpected adverse events to promptly. PLEASE NOTE all reportable AEs should be reported to the WCMC IRB as per WCMC AE reporting policy.

We will periodically report adverse events to the DSMB, in addition to reporting to the IRB as per Weill Cornell's policy.

19. Will you be using a medical monitor?

No

20. Please justify why no monitor is being used.

Medical information will be self-reported by participants during the baseline and follow-up research assessments.

21.

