### Primary Hypotheses:

- H1) More than 75% of Virtual PROTECT will attend each scheduled session.
- H2) Victims will have an average satisfaction (CSQ) score greater than 3 (out of 4) at 3, 6, and 12 weeks follow-up.
- H3) Community clinicians (LCSW) will have an average satisfaction (CSQ) score greater than 3 (out of 4) at the end of the project.

Secondary Hypotheses: Compared to EM/PROTECT (9 sessions, in-person), Virtual PROTECT participants will have: SH1) greater reduction (effect size) and clinically significant reduction in depression ( $\Delta$  MADRS  $\geq$ 3 pts by 12 weeks); SH2) improved quality of life (Primary Outcome:

WHOQOL-BRF).

In addition, to the above comparison, we will compare Virtual PROTECT with a historical comparison group (EM/MH, N=16) who received elder mistreatment services plus mental health referral as part of the first project.

**Power analysis:** The primary goal of this study is to establish the acceptability of Virtual PROTECT and obtain preliminary estimates of effect sizes for the improvement in depressive symptoms among Virtual PROTECT participants compared to PROTECT participants. Therefore, we estimated that with 40 Virtual-PROTECT participants, we will have a 95% confidence interval width of 24% for the acceptability (assuming a benchmark of 75%). With 40 Virtual PROTECT and 24 EM/PROTECT (in-person) participants, we can obtain an estimate of the difference in reduction of depression (MADRS) over the course of treatment between the two treatment groups with a 95% confidence interval half-width of 3.0 points. Therefore, we have adequate sample size to test our acceptability hypotheses and obtain a preliminary estimate of effect size with reasonable confidence in order to carry out an adequate powered trial.

**Aim 1. Finalize the Manual and Training:** We will finalize the EM/PROTECT Manual and use it to train Licensed Clinical Social Workers (LCSWs) at each EM agency. We will record the training hours needed to achieve certification in EM/PROTECT, the success rate of LCSWs in achieving certification and problems encountered during this process.

**Aim 2. PROTECT Operations Manual:** We will create an Operations Manual with the staff of EM agencies describing how PROTECT will be integrated into the agency, i.e. communication between EM staff, LCSWs, and research staff, PHQ-9 tracking and hand-off, and review of ongoing activities.

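### Participants who worsen may be removed from the study with no stated provision to keep assessing them, which would tend to flatter within-arm change; the effect on the historical contrasts is unknown

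*Combined protocol and SAP*

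**What the plan says.** The removal rule is in the Data and Safety Monitoring Plan: "if new psychiatric symptoms develop or change in severity, or the abuse situation escalates, we may recommend removal from the study". It is discretionary, and no expected frequency is given.

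The same section describes what follows. The operative clause pairs removal with referral, "we may recommend removal from the study and provide referrals for the appropriate treatment needed", and agency services carry on: "All EM victims will continue to receive EM resolution services from DFTA regardless of their participation or termination of participation in the study intervention". For those who leave, the answer to item 16 adds: "Referrals to external mental health agencies will be offered to participants who drop out of the study". None of these sentences mentions research assessments.

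Two other sentences in the section bear on the point. Symptoms are monitored: "Cornell research staff will assess changes in depressive symptoms at regular intervals". Removal is also not the only response to deterioration: "If any moderate to severe symptom changes (or new symptoms) are noted, we will consider alternative options to maximize the participant's well-being".

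The outcomes exposed are listed under Primary Hypotheses. H2 is a single-arm benchmark: "Victims will have an average satisfaction (CSQ) score greater than 3 (out of 4) at 3, 6, and 12 weeks follow-up". SH1 expects, relative to in-person EM/PROTECT, a "greater reduction (effect size) and clinically significant reduction in depression" with a 3-point MADRS threshold by 12 weeks. SH2 concerns WHOQOL. The Power analysis paragraph and Aims 3 to 5 state no analysis population, missing-data method or dropout allowance.

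**The concern.** The trigger for removal is either the outcome domain itself (psychiatric symptoms) or the stressor that drives it (the abuse). If assessments stop when someone is removed, later data are missing because that person is doing badly. A mean over those who remain then describes a group from which some of the failures have been taken out.

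This matters most where there is no comparator. H2 tests a mean CSQ against a fixed value of 3, and within-arm MADRS and WHOQOL change are read directly, so nothing offsets selective loss. The sample is 40, so four removals are already 10%. A confidence interval would not show the problem, because losing a few people hardly changes its width.

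**Working it through.** **Inputs from the documents.** Virtual PROTECT n = 40 and historical in-person EM/PROTECT n = 24; stated 95% half-width 3.0 MADRS points (Power analysis). CSQ benchmark above 3 of 4 (H2).

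**Assumed inputs.** The documents give no removal rate and no outcomes for removed participants. I take the fraction removed, d, as 5%, 10% or 20% (2, 4 or 8 of 40). The gap in mean MADRS improvement between retained and removed participants is taken as 5, 10 or 15 points. For orientation, retained participants improving by 8 and removed ones unchanged gives a gap of 8; removed ones worsening by 4 gives a gap of 12.

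**1. The plan's own precision figure.** No SD is stated, so the half-width of 3.0 cannot be independently reproduced. It implies SD = 3.0 / (1.96 × √(1/40 + 1/24)) = 3.0 / (1.96 × 0.2582) ≈ 5.9. With that SD, losing 20% of the new arm (32 vs 24) gives a half-width of 3.14. Losing 20% of both groups gives 3.35. The issue is bias, not precision.

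**2. Within-arm MADRS bias for a mean over retained participants only.**

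All-participant mean improvement = (1 − d) × retained mean + d × removed mean.

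Bias = retained mean − all-participant mean = d × gap.

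| Removed | Gap 5 | Gap 10 | Gap 15 |
|---|---|---|---|
| 5% | 0.25 | 0.5 | 0.75 |
| 10% | 0.5 | 1.0 | 1.5 |
| 20% | 1.0 | 2.0 | 3.0 |

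WHOQOL follows the same formula, but the documents give nothing from which to set a scale.

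**3. CSQ (H2).** Same formula, with assumed gaps of 0.5, 1.0 and 1.5 on the 4-point scale. At 10% removed the mean is overstated by 0.05, 0.10 or 0.15; at 20% by 0.10, 0.20 or 0.30. With 20% removed and a gap of 1.0, an observed mean of 3.1 corresponds to 3.1 − 0.2 = 2.9 in all participants, which falls below the benchmark. This needs removed participants to be less satisfied, which is an inference.

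**4. Contrast with a historical group (SH1, SH2).** If the gap is the same in both groups, bias in the difference = gap × (d in Virtual PROTECT − d in the historical group). With a MADRS gap of 10:

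- 10% vs 10%: 0
- 20% vs 10%: +1.0
- 10% vs 20%: −1.0

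The sign turns on a removal rate that the documents do not report.

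**5. Effect of continued assessment.** For anyone removed but still assessed, the contribution to d is zero, so the bias from that route disappears.

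**The case against.** The strongest reply is that the plan does not actually say assessments end. Removal is something staff may recommend, other responses are foreseen, and the sentence after the removal rule speaks of ending participation in the intervention. The monitoring section is also an incomplete form in the published text, and no assessment schedule is shown. This stands in part: it is an inference that data collection stops at removal. But the two expressions are never distinguished, and nothing tells staff to go on assessing, so clarification is needed on either reading.

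Second, the arithmetic assumes means over retained participants, and no analysis model is stated. Symptoms are assessed at regular intervals, so worsening may be recorded before removal. A likelihood-based repeated-measures model would then use that record, and the bias would be smaller than d × gap. This stands. For CSQ, the week 3 and week 6 scores may also precede removal.

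Third, a reader might infer that the comparative results, and the effect estimate meant to plan the next trial, are inflated. The documents do not support that. Those estimates are contrasts with historical groups whose removal rates and rules are not given; with equal removal and equal gaps the bias cancels.

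Fourth, a reader might set a within-arm bias of, say, 1.2 points (10% removed, gap 12) against the 3-point threshold and call it 40%. That mixes two quantities: the threshold sits in a between-group hypothesis.

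Finally, the rule's wording on change in severity literally covers improvement as well. Its pairing with referral makes worsening the natural reading.

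**Conclusion.** The point holds in limited form. The plan permits removal from the study for reasons tied to the outcome and does not say that outcome assessment continues. Within-arm MADRS and WHOQOL change would tend to look better than they are. So would mean CSQ, provided those who worsen are less satisfied.

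The size cannot be established. The illustrative within-arm MADRS figure is 0.5 to 1.5 points at 10% removed. It rests on an assumed removal rate, assumed gaps of 5 to 15 points and an analysis of retained participants only; it shrinks if worsening is captured before removal and used in the model. No direction can be claimed for SH1, SH2 or the planning estimate. The change is worth making because it is cheap and leaves the clinical decision alone, not because a large bias has been shown.

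**What to change.** Leave the removal and referral decision as it is, and change only data collection and analysis:

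- State that ending study therapy is distinct from leaving the study. A participant whose therapy ends for these reasons is asked, with consent, to complete the remaining scheduled MADRS, WHOQOL and CSQ assessments by phone or video.
- Record the date and reason for every removal or withdrawal.
- Analyse all enrolled participants, using all available assessments.
- Add one sensitivity analysis for missing week-12 MADRS, for example assigning no improvement from baseline, and apply the same rule to the historical groups where their data allow.

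The cost is a short protocol addition and a few extra interviews by existing research staff. Some of these participants will be distressed and may decline, and continued agency services do not guarantee research contact. The resulting mean may be less favourable. For anyone already removed, the analysis steps can still be applied.
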